Eyes with \geq 0.75 and \leq 2.5 diopters (D) of keratometric cylinder were randomly assigned to receive either the LAL or a commercially available, posterior chamber, non-accommodating, control monofocal IOL. Six hundred eyes were implanted with 403 eyes randomized to the LAL group and 197 eyes to the Control group.

⁸ Hamill E, Wang L, Chopra H, Hill W, Koch D. Intraocular lens power calculations in eyes with previous hyperopic laser in situ keratomileusis or photorefractive keratectomy. J Cataract Refract Surg 2017; 43:189-194.

⁹ https://www.reviewofophthalmology.com/article/post-refractive-cataract-choosing-lens-and-target

Co-primary effectiveness endpoints included percent reduction in manifest cylinder, percent mean absolute reduction in manifest refraction spherical equivalent (MRSE), and rotation of the LAL. All primary effectiveness endpoints compared pre-adjustment (LAL) or 17-21 days (Control) to 6 months postoperatively and the first two endpoints compared results between the LAL and Control groups. All three co-primary effectiveness endpoints were met with a p-value <0.0001. The difference in means for percent reduction in manifest cylinder was 54.7%, with a p-value <0.0001. The difference in means for percent reduction in absolute MRSE was 41.1% with a p-value <0.0001. Rotation of the LAL of ≤5 degrees was observed in 96.1% of LAL implanted eyes with both the upper and lower bound of the 95% confidence interval exceeding the requirement of 90%.

100% of eyes in both the LAL and Control groups had BSCVA of 20/40 or better, exceeding the historic grid rate of 92.5% (ISO 11979-7). The incidence of sight-threatening complications and adverse events for the LAL and Control groups were also below the threshold rates calculated from the 1-year historical grid for intraocular lenses (ISO 11979-7, Ophthalmic implants- Intraocular lenses- Part 7: Clinical investigations) except for the category of Secondary Surgical Interventions (SSI), which was significantly higher than the historical rate (p<.05).

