5 OUTCOME PARAMETERS

5.1 EFFECTIVENESS PARAMETER

Primary Endpoints

- Magnitude of manifest cylinder (MRCYL) at Postop Month 6
- Absolute Manifest Refraction Spherical Equivalent (MRSE) at Postop Month 6
- Outcome of best corrected distance visual acuity (BCDVA) of 20/40 or better at Postop Month 6

The MRCYL and MRSE outcomes will be compared between the two study groups, LAL and Control.

Per ISO 11979-7:2014 (E), one-sided upper 95% confidence limit of the percentage of LAL implanted eyes with BCDVA of 20/40 or better at Postop Month 6 is higher than the performance rate of 92.5%. It should be noted that all three effectiveness endpoints must be statistically significant in order to conclude the effectiveness of the LAL. Therefore, no additional significance level adjustment will be performed for these three primary endpoints.

Secondary Endpoints

- Uncorrected distance visual acuity (UCDVA) at Postop Month 6
- UCDVA at Postop Month 6 for subjects measured with keratometric cylinder (Kcyl) <0.75 D in both eyes at the preoperative examination.

The UCDVA outcomes will be compared between the two study groups, LAL and Control.

The secondary effectiveness endpoints will not be tested unless all three primary effectiveness endpoints are statistically significant. Due to this step-down approach, no additional adjustment will be made for the significance levels.

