8 STATISTICAL METHODS

8.1 SAMPLE SIZE CALCULATION

The sample size of up to 120 subjects with implantation of the LAL attempted in the primary eye for this study is based on the statistical tests on effectiveness endpoints described below. Safety of the LAL was studied under RxSight's premarket approval application (PMA) P160055 which was approved by the Center for Devices and Radiological Health (CDRH) of the Food and Drug Administration (FDA) on November 22, 2017.

Primary Effectiveness Endpoints

1. Magnitude of Manifest Cylinder (MRCYL) at Postop Month 6

H0: $\mu_{\Delta MRCYL} = 0$ versus Ha: $\mu_{\Delta MRCYL} < 0$ with a one-side significance level of 0.025, where $\mu_{\Delta MRCYL}$ is the mean of difference in MRCYL ($\Delta MRCYL$) at Postop Month 6 between the LAL eye and Control eye of bilateral subjects. The $\Delta MRCYL$ for each subject equals MRCYL of the LAL eye minus MRCYL of the Control eye. Since the magnitude of MRCYL will be used in the calculation, a negative $\Delta MRCYL$ represents a better outcome in the LAL eye than that in the Control eye.

Per the previous PMA clinical study, the standard deviation of the MRCYL at Postop Month 6 is 0.37 D for the LAL group and 0.62D for the Control group. Assuming that the MRCYL measurement of the two eyes of a subject are independent, the estimated standard deviation of Δ MRCYL is 0.73 (= square-root of the sum of 0.37² and 0.62²). It is expected that the postoperative MRCYL of the post-LASIK or other corneal refractive surgery eyes may have more variation, the standard deviation of Δ MRCYL is estimated as 1.00 D (about 1.5 times of the estimation based on the PMA observations) for sample size calculation. Based on the one-sided one-sample t-test (i.e. paired t-test) with a significance level of 0.025, a sample size of 77 subjects can provide a statistical power of 90% if the true $\mu_{\Delta MRCYL}$ at Postop Month 6 is -0.375 D.

2. Absolute Manifest Refraction Spherical Equivalent (MRSE) at Postop Month 6

H0: $\mu_{\Delta|MRSE|} = 0$ versus Ha: $\mu_{\Delta|MRSE|} < 0$ with a one-side significance level of 0.025, where $\mu_{\Delta|MRSE|}$ is the mean difference in absolute MRSE ($\Delta|MRSE|$) at Postop Month 6 between two eyes of bilateral subjects. The $\Delta|MRSE|$ equals |MRSE| of LAL eye minuses |MRSE| of Control eye. A negative $\Delta|MRSE|$ represents a better outcome in the LAL eye than that in the Control eye.

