Vector differences between the intended cylinder change and the achieved cylinder change will be calculated and summarized descriptively. In eyes for which no cylinder adjustment was attempted, the intended change will be considered zero and the entire change from Week 3 will be treated as an error. The summary will be provided for the LAL-eye and control eye separately. The difference in the vector length between the two eyes (= LAL-eye minus Control-eye) will be calculated for each subject and summarized descriptively at each visit.

Additionally, for the LAL eyes, a scatter plot will be presented showing the vector length of the change between the vector cylinder at the Postop Week 3 and Postop Month 6 visit as a

function of intended cylinder change and as a function of intended MRSE change. In order to evaluate the MRSE treatment effect on the cylindrical outcome, a regression analysis on the vector length with the intended cylinder correction and intended MRSE correction as independent factors will be performed. The regression residual will be checked for the model fitting.

Refractive Cylinder Stability

Refractive cylinder stability will be presented for consistent cohort and eyes with two consecutive visits. The following statistics will be calculated.

- Percentage of eyes that achieve change of ≤ 1.00 D of refractive cylinder;
- Percentage of eyes that achieve change of \leq 0.50 D of refractive cylinder;
- Mean MRCYL change between two visits and the corresponding 95% confidence interval, mean change per month, and mean change per year

MRSE

MRSE and change in MRSE from Postop Week 3 will be summarized by the descriptive statistics for continuous outcomes (such as mean and standard deviation) for each visit. The number and percent of eyes with an MRSE of $\leq \pm 0.25$ D, ± 0.50 , ± 0.75 D, ± 1.0 D, and ± 2.0 D will be reported for each visit. For each subject, the difference in the MRSE between two eyes (= LAL-eye – Control-eye) at Postop Week 3 and beyond will be calculated and the difference will be summarized by using descriptive statistics for continuous variables.

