For the contrast sensitivity (in log units) at each spatial frequency level under each of the four test conditions (photopic with and without glare and mesopic with and without glare) at Postop Week 3 and Postop Month 6 will be summarized by mean, standard deviation, median, minimum and maximum for the eyes participated in the contrast sensitivity substudy. The number and percent of eyes that cannot see any plate will be presented.

The mean of "within-eye" loss of contrast sensitivity from Postop Week 3 to Postop Month 6 will be provided with the 1-sided 95% confidence interval for each spatial frequency. The percentage of eyes showing > 0.3 log unit loss at two or more spatial frequencies will be calculated.

Increased Astigmatism

Number and percent of eyes with increased astigmatism from Postop Week 3 will be reported at each postoperative visit

Subjective Symptoms and Complaints

Number and percent of eyes will be summarized for each reported subjective symptom.

Other Ocular Examinations

Slit lamp and fundus exam findings and IOP including changes will be summarized descriptively. Number of subjects with fundus exam changes from the pre-op and Postop Week 3 evaluation will be summarized.

Endothelial Cell Density (ECD) and Morphology Data

Specular Microscopy data includes endothelial cell density, hexagonality and coefficient of variation. These endpoints will be summarized by mean, standard deviation, 95% CI of the mean, minimum and maximum. The change in ECD and percent change in ECD from preoperative will be summarized in the same manner. Additionally, ECD change and ECD percent change for each eye will be calculated between Preoperative and Postop Week 3 and between Postop Week 3 and Postop Month 6. These changes will be summarized by mean, standard deviation, 95% CI for mean, minimum, and maximum. Additionally, at Postop Week 3 and Postop Month 6, the number and percent of eyes with an ECD of < 1500 cells/mm² and number and percent of eyes with an ECD change from baseline \leq -25% (i.e. and an ECD loss of \geq 25%) along with the 95% confidence interval of the percentage derived per binomial distribution will be calculated for the LAL eyes and Control eyes separately.

The percent ECD loss (%ECL) at Postop Month 6 for each eye and the difference between %ECL (Δ %ECL) at Postop Month 6 for each subject are derived as follows:

%ECL = (ECD at Preop – ECD at Postop Month 6)
$$\div$$

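### Cylinder stability between visits is summarised on cylinder magnitude, so the descriptive stability figures can match or overstate vector-based stability but never understate it

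*Combined protocol and SAP*

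**What the plan says.** Section 8.5.4, Refractive Cylinder Stability, sets the scope as "Refractive cylinder stability will be presented for consistent cohort and eyes with two consecutive visits". It then lists three statistics:

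- "Percentage of eyes that achieve change of ≤ 1.00 D of refractive cylinder";
- the same percentage with the limit at "0.50 D of refractive cylinder";
- as the third and only averaged item, "Mean MRCYL change between two visits and the corresponding 95% confidence interval, mean change per month, and mean change per year".

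Section 5.1 defines the first primary endpoint as "Magnitude of manifest cylinder (MRCYL) at Postop Month 6". Section 8.1 confirms the scalar meaning when it forms the between-eye difference: "Since the magnitude of MRCYL will be used in the calculation". None of the three stability statistics mentions axis or vector.

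The Vector Difference paragraphs just above do use vectors. They compare intended with achieved cylinder change and plot, for LAL eyes, the vector length of the change from Week 3 to Month 6. The reference there is Week 3, and the purpose is treatment accuracy. No vector change between consecutive visits is written anywhere in the visible text.

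**The concern.** Astigmatism has a magnitude and an axis. If change between visits is the difference of two magnitudes, an eye with the same cylinder power at a different axis shows no change. It falls inside both percentages and adds zero to the mean. The mean-change line is explicitly scalar. The percentage lines say refractive cylinder rather than MRCYL, but the plan names vectors when it means them, so the scalar reading is the natural one. If a vector was intended there, the text needs to say so.

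At stake is how the stability table can be read. Its percentages would be an upper bound on vector-based stability, with nothing beside them to show how far above it they lie.

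**Working it through.** The plan states no figure for this analysis, so there is nothing to reproduce. The check is geometric.

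**Inputs.** The limits of 0.50 D and 1.00 D come from 8.5.4. Residual cylinder after lock-in is not given; I assume 0.25 to 2.00 D, the top borrowed from the keratometric entry limit in 6.1. Axis variability between visits is not given either; I assume standard deviations of 10 and 20 degrees.

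**Step 1: direction.** Write the cylinder at two visits as double-angle vectors a and b. The triangle inequality gives | |a| − |b| | ≤ |a − b|. An eye within a limit by vector is therefore also within it by magnitude, and the magnitude percentage can only equal or exceed the vector percentage.

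**Step 2: size for one eye.** If magnitude stays at C and the axis shifts by t, magnitude change is 0 and vector change is 2C·sin(t).

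- C = 1.00 D, t = 30°: 2 × 1.00 × 0.500 = 1.00 D. By vector the eye fails the 0.50 D limit and sits exactly on the 1.00 D limit. By magnitude it scores 0.00 D.
- C = 0.75 D, t = 45°: 2 × 0.75 × 0.707 = 1.06 D, beyond both limits. By magnitude it scores 0.00 D.

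**Step 3: axis shift at which the vector change reaches each limit**, t = arcsin(limit / 2C):

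| C (D) | reaches 0.50 D | reaches 1.00 D |
|---|---|---|
| 0.25 | 90° | never |
| 0.50 | 30.0° | 90° |
| 0.75 | 19.5° | 41.8° |
| 1.00 | 14.5° | 30.0° |
| 1.50 | 9.6° | 19.5° |
| 2.00 | 7.2° | 14.5° |

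**Step 4: illustrative percentages.** Hold magnitude constant and let the axis shift be normal with mean 0. By magnitude, 100% of eyes pass the 0.50 D limit. By vector, simulation gives:

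| C (D) | SD 10° | SD 20° |
|---|---|---|
| 0.50 | 99.7% | 87% |
| 0.75 | 95% | 67% |
| 1.00 | 85% | 53% |

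Constant magnitude is the least favourable case for a scalar measure, so these gaps are not forecasts.

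**Step 5: does Vector Difference fill the gap?** Not between visits. Two visits can each show a vector error of 0.50 D from the intended change, yet lie 1.00 D apart if the errors point in opposite directions. Equal error lengths at successive visits therefore do not establish stability.

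**The case against.** Most of the case on the other side limits the size of the point, and much of it stands.

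**Lens rotation is often visible in magnitude.** A reader might infer that rotation of the adjusted lens goes uncounted. The documents do not support that. Manifest cylinder combines cornea and lens. If a lens that fully corrects L dioptres rotates by t, the residual rises from 0 to 2L·sin(t) in magnitude. With L = 1.50 D and t = 10° that is 0.52 D, which exceeds the 0.50 D limit by magnitude alone. What survives is partial understatement. Assume a 1.50 D cornea with an aligned 1.00 D correction, rotated 20°. The residual goes from 0.50 D to √(1.50² + 1.00² − 2 × 1.50 × 1.00 × cos 40°) = 0.98 D. Magnitude change is 0.48 D (passes 0.50 D); vector change is 2 × 1.00 × sin 20° = 0.68 D (fails).

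**The prior rotation result is reassuring.** Section 2.1 lists percent reductions in cylinder and MRSE "and rotation of the LAL" as co-primary endpoints of the earlier study. A reader might infer that, without a rotation endpoint here, axis change is the only remaining sign of instability. But the same section reports rotation of 5 degrees or less in 96.1% of LAL eyes. At 5° and an assumed L of 2.00 D, the vector change from rotation is 2 × 2.00 × sin 5° = 0.35 D, below both limits. Some assessment rows are also blacked out, so the absence of a rotation measure cannot be asserted. The larger axis shifts above are tied to no figure in the documents.

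**Nothing is decided on this table.** Cylinder stability is descriptive and has no pass criterion, unlike MRSE stability in the same section. This stands.

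**Vector Difference gives partial cover.** Axis change since Week 3 enters the vector error, fully so in eyes with no attempted cylinder adjustment. This stands, subject to Step 5.

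**The safety count is not affected.** A reader might extend the point to section 8.6: "Number and percent of eyes with increased astigmatism from Postop Week 3 will be reported at each postoperative visit". That does not follow. The same cylinder at a new axis is not increased astigmatism. Week 3 also precedes adjustment, so a vector count from that baseline would flag successful treatment: 1.25 D corrected to 0 is a vector change of 1.25 D.

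**Conclusion.** The point holds in a limited form. The mean-change statistic is a magnitude by definition, and the two percentages read most naturally the same way. For the percentages, any discrepancy from a vector measure runs in one direction, toward stability; that follows from geometry and needs no assumption. Its size cannot be estimated, because the documents give neither residual cylinder nor axis variability after lock-in. Under the assumed values, the share within 0.50 D would be overstated by less than 1 percentage point (0.50 D residual, SD 10°) to about 47 points (1.00 D residual, SD 20°), with constant magnitude throughout. At a constant 0.25 D residual no axis shift can take an eye past 0.50 D, so eyes with little residual are barely affected.

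No primary or secondary endpoint, hypothesis or sample size depends on this. It is a cheap improvement to a descriptive analysis.

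**What to change.** In 8.5.4, or in the detailed SAP that 8.2 says will be finalised before database lock:

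- Define the per-eye change in the 0.50 D and 1.00 D percentages as the length of the vector difference between two consecutive post-lock-in visits. The intervals already listed for MRSE stability (Months 1-2 to Month 3, Month 3 to Month 6) would serve. For control eyes use the matching visits; their schedule has no Months 1-2 visit, so the direct match is Month 3 to Month 6.
- Add mean change in J0 and J45 with 95% confidence intervals. These show systematic drift; the vector-length percentages show scatter, which can cancel in a mean.
- State the scale. If J0 and J45 are half-cylinder components, the length in cylinder dioptres is 2·√(ΔJ0² + ΔJ45²). For 1.00 D shifting 30°, the component changes are 0.25 and 0.433, giving 2 × 0.50 = 1.00 D.
- Keep change in MRCYL magnitude as a supportive line.
- Leave the increased-astigmatism count in 8.6 as it is.

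The cost is programming. The planned vector analyses already need the axis, so no new data are required. The downside is slightly less favourable percentages, part of which will be axis measurement noise at low cylinder; the supportive magnitude line helps the reader judge that.

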7.6 CLINICAL PARAMETERS

25. Adverse Events

The following study parameters will be assessed as specified here and in Table 2 and 3. Assessments will be performed using the techniques described in

1. Demographics 2. 3. 4. Ocular history including medications 5. Ocular Biometry: ACD and axial length (Optical or immersion A-scan biometry) 6. Subjective symptoms/complaints (subject reported) 7. 8. Corneal Topography 9. Autorefraction 10. Corneal Keratometry 11. Specular Microscopy 12. Uncorrected distance visual acuity (UCDVA) 13. Manifest Refraction 14. Best corrected distance visual acuity (BCDVA) 15. 16. 17. Distance corrected contrast sensitivity: Mesopic/Photopic with and w/o glare 18. 19. Intraocular pressure 20. Slit Lamp Examination 21. Dilated pupil diameter 22. Fundus Exam 23. Fundus Photos 24.

Table 2. Schedule of Visits and Clinical Parameters for Primary Study Eyes (LAL)

Table 2. Schedule of	V ISIUS	s and c	Clinic	ai Pai	ramet	ers ioi	r Prilli	iary S	stuay .	Lyes ((LAL))		
Visits	Preop OU	Operative LAL	Postop Day 1 LAL	Postop Week 1 LAL	Postop Week 3 LAL	Adjustment #2 (if needed)	Adjustment #3 (if needed)	Lock-in #1	Lock-in #2 (if needed)	Post Months 1-2	Postop Month 3 LAL	Postop Month 6 LAL	Postop Month 12 (if needed)	Unscheduled Visit ³
Demographics	X													
	X				X					X	X	X		
					X	X	X	X	X	X	X	X	X	
Ocular History Including Medications	X	X	X	X	X	X	X	X	X	X	X	X	X	
Ocular Biometry (ACD + Axial length)	X													
Subjective Symptoms/Complaints (Subject reported)			X	X	X	X	X	X	X	X	X	X	X	X
			X	X	X	X	X	X	X					
Corneal Topography	X				M									 
Autorefraction				X	M	X	X	X	X	X	M	M	X	
Corneal Keratometry	X				M							M		
Specular Microscopy	X				M							M		
Uncorrected distance visual acuity (UCDVA)	X		X	X	M	X	X	X	X	X	M	M	X	X
Manifest Refraction	X			X	M	X	X	X	X	X	M	M	X	X
Best corrected Visual Acuity Distance (BCDVA)	X			X	M	X	X	X	X	X	M	M	X	X
					M	X	X	X	X	X	M	M	X	
					M	X	X	X	X	X	M	M	X	
Distance Corrected Contrast Sensitivity (Mesopic/Photopic w and w/o glare)					M							M		
					X					X^2	X^2	X^2	X^2	

Visits	Preop OU	Operative LAL	Postop Day 1 LAL	Postop Week 1 LAL	Postop Week 3 LAL	Adjustment #2 (if needed)	Adjustment #3 (if needed)	Lock-in #1	Lock-in #2 (if needed)	Post Months 1-2	Postop Month 3 LAL	Postop Month 6 LAL	Postop Month 12 (if needed)	Unscheduled Visit ³
Intraocular Pressure	X		X	X	X	X	X	X	X	X	X	X	X	
Slit Lamp Exam	X		X	X	X	X	X	X	X	X	X	X	X	X
Dilated Pupil Diameter	X				X	X	X	X	X					

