The refractive stable point will be determined based on the five criteria described in Section F.3 of ANSI Z80.11-2012 document as follows:

- At least 95% of the treated eyes have a change ≤1.00 D of MRSE between the two refractions:
- The mean rate of change in MRSE, as determined by a paired analysis, is ≤ 0.5 D per year (0.04 D/month) over the same time period;
- The mean rate of change of MRSE decreases monotonically over time, with a projected asymptote of zero or a rate of change attributable to normal aging;
- The 95% confidence interval for mean rate of change includes zero or a rate of change attributable to normal aging.

The MRSE change between the following post-adjustment visit intervals will be presented.

- From Postop Months 1-2 to Postop Month 3
- From Postop Month 3 to Postop Month 6

Defocus Equivalent (DEQ)

The DEQ will be summarized descriptively at Postop Week 3 and beginning at Postop Months 1-2. The number and percent of eyes with DEQ \leq 0.5 D and 1.0 D will also be summarized at the corresponding visit.

Autorefraction

Autorefraction sphere, cylinder, and spherical equivalent will be summarized descriptively at each visit.

Since, for the LAL eyes, the light adjustment will be based on the manifest refraction, the following change in auto-refraction cylinder (Cyl) and reduction in auto-refraction spherical equivalent (SE) will be calculated for each LAL eye:

Change in Cyl = (Postop Month 6 autorefraction Cyl – Postop Week 3 MRCYL),

Change in SE = (Postop Month 6 autorefraction SE – Postop Week 3 MRSE)

The change in cylinder and the change in the spherical equivalent will be summarized descriptively by mean, standard deviation, median, minimum, and maximum.

UCDVA

UCDVA will be presented with the number and percent of eyes who fall into each category of UCDVA at each visit (e.g. 20/20 or better, 20/25 or better, 20/32 or better, etc.). The logMAR UCDVA will be summarized by descriptive statistics for continuous outcomes for each visit. Change in UCDVA from Postop Week 3 will be presented at each visit as categorical outcomes of "increase in 15 letters or more", "Increase in 10-14 letters", "Increase in 5-9 letters", "Decrease in 10-14 letters", and "Decrease in 15 letters or more". The change in logMAR UCDVA from Postop Week 3 will also be presented.

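### The planned change in autorefraction for LAL eyes is computed from a Week 3 manifest baseline, so label and formula disagree and the result carries the full offset between the two methods

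*Combined protocol and SAP*

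**What the plan says.** Section 8.5.4, under Autorefraction, first plans method-consistent summaries: "Autorefraction sphere, cylinder, and spherical equivalent will be summarized descriptively at each visit". It then gives a reason for a further analysis, "Since, for the LAL eyes, the light adjustment will be based on the manifest refraction", and states that "the following change in auto-refraction cylinder (Cyl) and reduction in auto-refraction spherical equivalent (SE) will be calculated for each LAL eye". The two definitions are:

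- "Change in Cyl = (Postop Month 6 autorefraction Cyl – Postop Week 3 MRCYL"
- "Change in SE = (Postop Month 6 autorefraction SE – Postop Week 3 MRSE"

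The abbreviation list defines MRCYL and MRSE as manifest refraction quantities. The planned output is limited: "The change in cylinder and the change in the spherical equivalent will be summarized descriptively by mean, standard deviation, median, minimum, and maximum".

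The Autorefraction rows of Table 2 (LAL eyes) and Table 3 (Control eyes) both carry an M at Week 3 and at Month 6. Section 4 names these as masked-examiner visits. Section 7.3.2 places the first light adjustment at the Week 3 visit.

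**The concern.** The text names a change in autorefraction, and the formula does not compute one. The follow-up value is autorefraction and the baseline is manifest refraction, so a systematic difference between the methods appears in the output as if the eye had changed. The stated reason explains the interest in the Week 3 manifest value but does not remove the offset.

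Two smaller mismatches sit in the same lines. The SE quantity is called a reduction, yet the formula gives a signed change, so shifts in opposite directions can cancel in the mean. Section 8.1 uses MRCYL as a magnitude, but nothing says whether autorefraction Cyl is also taken as a magnitude before the subtraction.

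At stake is how one supporting line can be read. Both refractive primary endpoints rest on manifest refraction, so a within-eye change measured by instrument would be useful supporting evidence. The mixed score does not provide it.

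**Working it through.** The plan attaches no figure to this line, so there is nothing to reproduce. The check is algebra, with assumed offsets put in.

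**Inputs**

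- Formulas: Section 8.5.4, as quoted above.
- Availability of Week 3 and Month 6 autorefraction: Tables 2 and 3.
- Offset between methods: not in the documents. Assumed range -0.50 to +0.50 D.

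**Step 1: decompose the planned score.** Let A be autorefraction, M manifest refraction, with subscripts 3 (Week 3) and 6 (Month 6), and let b = A - M in the same eye at the same visit.

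- Planned score: A6 - M3 = (A6 - A3) + (A3 - M3) = autorefraction change + b3.
- Equivalently: A6 - M3 = (M6 - M3) + (A6 - M6) = manifest change + b6.
- Like-for-like score: A6 - A3 = (M6 - M3) + (b6 - b3).

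The planned score carries one whole offset. The like-for-like score carries only the change in offset between visits, which is zero if the offset is constant.

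**Step 2: put numbers in.** With a constant offset, the planned mean is true change + b and the like-for-like mean is the true change.

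| True change (D) | Assumed b (D) | Planned formula | Like-for-like |
|---|---|---|---|
| 0 | -0.50 | -0.50 | 0.00 |
| 0 | -0.25 | -0.25 | 0.00 |
| 0 | +0.25 | +0.25 | 0.00 |
| 0 | +0.50 | +0.50 | 0.00 |
| -0.50 | -0.50 | -1.00 | -0.50 |
| -0.50 | +0.25 | -0.25 | -0.50 |
| -0.50 | +0.50 | 0.00 | -0.50 |

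A simulation of 200,000 eyes per scenario (assumed Week 3 SD 0.6 D, measurement error SD 0.25 D) agreed with these means to within 0.002 D. A real change of -0.50 D can be hidden or doubled, depending on a sign that the documents do not give.

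**Step 3: what other planned output recovers.** By-visit summaries give the means of A3 and A6, and the manifest summaries give the mean of M3. In eyes seen at both visits:

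- mean A6 - mean A3 = mean like-for-like change;
- mean A3 - mean M3 = mean offset at Week 3 (for cylinder, only if both are on the same sign convention).

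The spread is not recovered. SD(A6 - A3)^2 = SD(A6)^2 + SD(A3)^2 - 2 cov(A6, A3), and by-visit summaries contain no covariance. The median, minimum and maximum of the per-eye change cannot be derived from them either.

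**Step 4: what depends on the score.** The primary endpoints are MRCYL, absolute MRSE and BCDVA; the secondary endpoints are UCDVA. None uses autorefraction. As a context check, the paired t-test sample sizes in Section 8.1 reproduce exactly: 77, 67 and 60, with power 0.901, 0.902 and 0.905. None takes this score as an input.

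**The case against.** The strongest defence is that the manifest baseline is deliberate and disclosed. The light adjustment is planned from the manifest refraction, so the score can be read as the Month 6 instrument reading set against the refraction that was treated. That reading is legitimate and is a reason to allow the mixed quantity as a second line. It does not make the quantity a change in autorefraction, which is what the text calls it.

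The second defence is that autorefraction by visit is already planned, as is same-method manifest change from Week 3. This stands for means. A reader might infer that the plan cannot separate lens adjustment from instrument offset. That would be true of the single mixed score but not of the plan as a whole, because the mean like-for-like change and the mean offset can largely be read off. Only the paired spread is lost.

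Third, the remedy is conditional. Section 7.1.1 describes a lens whose shape is altered by light treatment, and that treatment falls between the two visits. The documents do not establish that the offset stays constant across it. This stands, and it is why the same-visit difference between methods should be reported if the mixed score is kept.

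**Conclusion.** The point holds as a mismatch between label and formula in one descriptive line, with a known mechanism and an unknown size. The mixed mean equals the true change plus the mean autorefraction-minus-manifest offset, one for one. The -0.50 to +0.50 D range is an assumption, and the offset could favour or penalise the LAL. The priority is low, since no endpoint, test, error rate or sample size is affected.

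Two stronger readings are tempting and are not supported:

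- A reader might infer that the offset will be reported as a treatment effect. The plan attaches no test, confidence interval, Control contrast or effect claim to this line.
- A reader might set the offset against the planned 0.25 D effect on absolute MRSE in Section 8.1. That figure is a between-eye difference in absolute values, whereas this score is a within-eye change in signed SE. The plan combines them in no inference, so the comparison does not measure impact.

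Nor do the documents formally assign autorefraction the role of objective check on the primary endpoints. Its value as supporting evidence is a matter of judgement.

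**What to change.** In Section 8.5.4, or in the detailed SAP that Section 8.2 says will be finalised before database lock:

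- Define Change in Cyl as Month 6 autorefraction cylinder magnitude minus Week 3 autorefraction cylinder magnitude, stating that magnitudes are used, as for MRCYL.
- Define Change in SE as Month 6 autorefraction SE minus Week 3 autorefraction SE, and call it a change rather than a reduction.
- Report both for LAL and Control eyes with the descriptive statistics already listed.
- If the mixed quantity is kept, relabel it as Month 6 autorefraction versus Week 3 manifest refraction. Beside it, report the same-visit autorefraction-minus-manifest difference at Week 3 and at Month 6, so that the offset and any shift in it are visible.

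The cost is two rewritten formulas and a few table rows. No new measurement is needed, because both eye groups already have autorefraction scheduled at both visits.
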